## **14 Publication Authorship Requirements**

Authorship for any Otsuka-sponsored publications resulting from the conduct of this trial will be based on International Committee of Medical Journal Editors (ICMJE) authorship criteria (<http://www.icmje.org/recommendations>).

According to ICMJE guidelines, one may be considered an author only if the following criteria are met:

1. Substantial contributions to the conception or design of the work; or the acquisition, analysis, or interpretation of data for the work; AND
2. Drafting the work or revising it critically for important intellectual content; AND
3. Final approval of the version to be published; AND
4. Agreement to be accountable for all aspects of the work in ensuring that questions related to the accuracy or integrity of any part of the work are appropriately investigated and resolved.

All authors must meet the above criteria, and all who qualify for authorship based on the above criteria should be listed as authors.

Investigators or other trial participants who do not qualify for authorship may be acknowledged in publications resulting from the trial. By agreeing to participate in the trial, investigators or other trial participants consent to such acknowledgement in any publications resulting from its conduct.

Protocol 323-201-00003

- [Redacted list item 1]
- [Redacted list item 2]
- [Redacted list item 3]
- [Redacted list item 4]
- [Redacted list item 5]
- [Redacted list item 6]
- [Redacted list item 7]

[figure not shown]
[Redacted text block]

[Redacted]	[Redacted]	[Redacted]
[Redacted]	[Redacted]	[Redacted]
[Redacted]	[Redacted]	[Redacted]

Protocol 323-201-00003

Protocol 323-201-00003

Protocol 323-201-00003

[REDACTED]

[REDACTED]

[REDACTED]

[REDACTED]

Protocol 323-201-00003

[Redacted text block]

[Redacted text block]

[Redacted]	[Redacted]	[Redacted]
[Redacted]	[Redacted]	[Redacted]
[Redacted]	[Redacted]	[Redacted]
[Redacted]	[Redacted]	[Redacted]
[Redacted]	[Redacted]	[Redacted]

Protocol 323-201-00003

[REDACTED]

[REDACTED]

[REDACTED]

[REDACTED]

[figure not shown]
Protocol 323-201-00003

[Redacted text block]

[Redacted text block]

[Redacted]	[Redacted]	[Redacted]
[Redacted]	[Redacted]	[Redacted]

Protocol 323-201-00003

Protocol 323-201-00003

[REDACTED]

[REDACTED]

[REDACTED]

[REDACTED]

Protocol 323-201-00003

[REDACTED]

[REDACTED]

[REDACTED]	[REDACTED]	[REDACTED]	[REDACTED]
------------	------------	------------	------------

[REDACTED]

Protocol 323-201-00003

# **List of Abbreviations and Definition of Terms**

Abbroviotion	Definition
Abbreviation AE	Adverse event
ALP	Alkaline phosphatase
ALT	Alanine aminotransferase
AST	Aspartate aminotransferase
AUC	Area under the concentration-time curve
	Area under the concentration-time curve from zero to 24 hours
AUC 24h AUC∞	Area under the concentration-time curve from time zero to infinity
	•
$\mathrm{AUC}_{ au}$	Area under the concentration-time curve calculated over the dosing interval at steady-state
AUCt	Area under the concentration-time curve from time zero to time t (the last observable concentration)
BDQ	Bedaquiline
CRF	Case report form
CFU	Colony-forming unit
CRO	Clinical Research Organization
CLss/F	Apparent clearance of drug from plasma at steady-s
Cmax	Maximum (peak) plasma concentation
Cmax,ss	Cmax during the dosing interval at steady-state
CYP	Cytochrome P450
DAIDS	Division of AIDS
DNA	Deoxyribonucleic acid
EBA	Early bactericidal activity
ECG	Electrocardiogram
EDC	Electronic data capture
ELISA	Enzyme-linked immunosorbent assay
Emax	Maximum effect
ET	Early Termination
EU	European Union
EudraCT	European Clinical Trial Data Base
FDA	(United States) Food and Drug Administration
GCP	Good Clinical Practice
GGT	Gamma glutamyl transferase
hCG	Human chorionic gonadotropin
IB	Investigator's brochure
ICF	Informed consent form
ICH	International Conference on Harmonisation
ICMJE	International Committee of Medical Journal Editors
IEC	Independent ethics committee
IMP	Investigational medicinal product
IND	Investigative new drug
IRB	Institutional review board
IRE	Immediately reportable event
LAM	Lipoarabinomannan

M2 N-monodesmethyl metabolite

MedDRA Medical Dictionary for Regulatory Activities
MGIT Mycobacteria Growth Indicator Tube®
MIC Minimum inhibitory concentration

MITT Modified Intent to Treat

OPDC Otsuka Pharmaceutical Development & Commercialization, Inc.

PD Pharmacodynamic
PE Physical examination
PK Pharmacokinetic(s)
PQC Product quality complaint

QD Once daily

QTcB Corrected QT interval using Bazett's method QTcF Corrected QT interval using Fridericia's method

RBC Red blood cell

RHEZ Rifampicin, isoniazid, ethambutol, and pyrazinamide

SAD Single ascending dose SAE Serious adverse event SD Standard Deviation

t1/2,z Terminal-phase elimination half-life

TB Tuberculosis

TEAE Treatment-emergent adverse event

TTD Time to detection

US or USA United States or United States of America

ULN Upper limit of normal WBC White blood cell

WOCBP Women of childbearing potential

XDR Extensively drug-resistant

### 1 Introduction

This statistical analysis plan (SAP) documents the statistical methodology and data analysis algorithms and conventions to be applied for the analysis of clinical trial data of trial 323-201-00003 for compound OPC-167832. The original protocol was dated 26 Feb 2018. Amendment 1, 2, 3, 4 and 5 of the protocol occurred on 29 Jan 2019, 25 Oct 2019, 20 Dec 2019, 17 August 2020, and 21 May 2021. All amendments to the protocol are taken into consideration in the SAP.

There is a separate PK plan with details on the analyses of the PK endpoints.

# 2 Trial Objectives

# 2.1 Primary Objective

# 2.1.1 Stage 1

To evaluate the efficacy, pharmacokinetics (PK), safety, and tolerability of multiple ascending oral doses of OPC-167832 compared with the administration of RHEZ in subjects with uncomplicated, smear-positive, drug-susceptible pulmonary TB.

# 2.1.2 Stage 2

- To evaluate the safety and tolerability of multiple oral doses of OPC-167832 when administered with delamanid and/or bedaquiline (BDQ) compared with the administration of RHEZ alone in subjects with uncomplicated, smear-positive, drug-susceptible pulmonary TB.
- To evaluate the PK of OPC-167832 and delamanid, and/or BDQ after coadministration.

# 2.2 Secondary Objectives

# 2.2.1 Stage 1

- To evaluate the relationship between OPC-167832 exposure and efficacy determined by changes of sputum lipoarabinomannan (LAM) and Mycobacteria Growth Indicator Tube® (MGIT) time to detection (TTD), after multiple ascending oral doses of OPC-167832.
- To evaluate the relationship between QT interval and plasma concentrations of OPC-167832.

# 2.2.2 Stage 2

- To evaluate the efficacy of OPC-167832 when administered with delamanid and/or BDQ compared with the administration of RHEZ alone in subjects with uncomplicated, smear-positive, drug susceptible pulmonary TB.
- To evaluate the relationship between OPC-167832 exposure and efficacy determined by changes of sputum LAM and MGIT time to detection after OPC-167832 when administered with delamanid and/or BDQ.
- To evaluate the relationship between QT interval and plasma concentrations of OPC-167832 when administered with delamanid and/or BDQ.

Statistical Analysis Plan

• To evaluate the PK of DM-6705 after coadministration of OPC-167832 and delamanid and/or BDQ.

# 2.2.3 Stage 1 and Stage 2

To evaluate the efficacy, safety, and tolerability of OPC-167832 when administered with delamanid and/or BDQ (data derived from stage 2) compared with the administration of OPC-167832 alone (data derived from stage 1).

# 3 Trial Design

# 3.1 Type/Design of Trial

## 3.1.1 Stage 1

Stage 1 will be a randomized, open-label, active controlled, multiple ascending dose stage in approximately 72 subjects. Dosing is planned to be conducted in 4 sequential cohorts of 18 subjects each:

- Cohort 1: 10 mg OPC-167832 or RHEZ (14 OPC-167832 subjects and 4 RHEZ subjects)
- Cohort 2: 30 mg OPC-167832 or RHEZ (14 OPC-167832 subjects and 4 RHEZ subjects)
- Cohort 3: 90 mg OPC-167832 or RHEZ (14 OPC-167832 subjects and 4 RHEZ subjects)
- Cohort 4: 3 mg OPC-167832 or RHEZ (14 OPC-167832 subjects and 4 RHEZ subjects)

Subjects who signed the informed consent form (ICF) will be admitted to the trial site at screening. Subjects will be screened for up to 4 days (Days -6 to -3) prior to the start of the Day -2 assessments. Screening can be extended up to 7 days. Subjects randomized to OPC-167832 will receive once daily (QD) oral doses of investigational medicinal product (IMP; OPC 167832) from Day 1 through Day 14. After Day 14, the subjects will receive treatment for pulmonary TB according to the local standard of care regimen (RHEZ). In subjects with no clinical indication to start RHEZ immediately, commencement of RHEZ can be delayed for up to 3 days (Days 15, 16, and 17) under close supervision in the trial site hospital ward.

Subjects randomized to RHEZ will receive QD oral doses of RHEZ from Day 1 through Day 20.

Subjects will be discharged on Day 20 once all safety assessments have been completed and all PK samples have been collected.

The safety, tolerability, PK, and efficacy (results from Otsuka TB LAM enzyme-linked immunosorbent assay [ELISA] only) data from each cohort will be reviewed by the trial review team at the end of each cohort. Once all the data for dose selection for the next cohort is available, the data collected from each cohort will be provided to the trial review team. The data will be evaluated to determine if (i) the dose level for the next cohort will be escalated, (ii) the dose level from the previous cohort will be repeated, or (iii) the dose level will be decreased. The dose of OPC-167832 will not exceed the highest tolerated dose studied in the single ascending dose trial, i.e., 480 mg.

Decisions to proceed to the next dose level should be based on, but not limited to, the following safety aspects:

- No death assessed as related to OPC 167832
- No more than 2 subjects with Grade 4/5 AEs ("Division of AIDS [DAIDS] Table for Grading the Severity of Adult and Pediatric AEs") assessed as related to OPC 167832.

# 3.1.2 Stage 2

The dose of OPC-167832 for Stage 2 has been determined based on the safety, tolerability, PK and efficacy data from Stage 1 of this trial. Based on the Stage 1 PK/PD analysis of OPC-167832 plasma concentrations and reduction in log10CFU/mL, a dose lower than the current 30 mg specified in the protocol may be considered, provided it can offer similar potential for efficacy as the 30 mg dose.

Stage 2 will be a randomized, open-label, active-controlled, parallel group comparison stage comprising of 46 subjects (subjects who were randomized in stage 1 cannot enroll in stage 2).

Subjects who signed ICF will be admitted to the trial site at screening. Subjects will be screened for 4-7 days prior to the start of Day -2 assessments. Eligible subjects will be housed at the trial site until discharge or early termination. All subjects enrolled during this stage of the trial will be randomized prior to first dosing on Day 1 to one of the following 4 treatments in a ratio of 14:14:14:4:

- 30 mg OPC-167832 and 300 mg delamanid QD (14 subjects)
- 30 mg OPC-167832 and 400 mg BDQ QD (14 subjects)
- 30 mg OPC-167832 and 300 mg delamanid and 400 mg BDQ QD (14 subjects)

• RHEZ QD (4 subjects)

Subjects receiving BDQ will take a loading dose of 700 mg BDQ on Day 1 and 500 mg on Day 2. The dose of BDQ will be 400 mg QD for days 3 to 14.

Subjects will be centrally randomized through an interactive voice response system with no stratification.

Subjects randomized to OPC-167832 and/or delamanid and/or BDQ will receive QD oral doses of IMP (OPC-167832 and/or delamanid and/or BDQ) from Day 1 through Day 14. After Day 14, the subjects will receive treatment for pulmonary TB according to the local standard of care regimen (RHEZ). In subjects with no clinical indication to start RHEZ immediately, commencement of RHEZ can be delayed for up to 3 days (Days 15, 16, and 17) under close supervision in the trial site hospital ward.

Subjects randomized to RHEZ will receive QD oral doses of RHEZ from Day 1 through Day 20.

Subjects will be discharged on Day 20 once all safety assessments have been completed and all PK samples have been collected.

#### 3.2 Trial Treatments

# 3.2.1 Investigational Medicinal Products

### 3.2.1.1 Stage 1

Subjects randomized to OPC-167832 will receive QD oral doses of IMP (OPC-167832) from Day 1 through Day 14.

The planned dose escalation steps of OPC-167832 for Cohorts 1 to 4 are 10, 30, 90, and 3 mg, respectively. The IMP will be administered with 240 mL of still (noncarbonated) water at room temperature, within 5 minutes after the completion of a meal.

#### 3.2.1.2 Stage 2

Subjects randomized to 30 mg OPC-167832 and 300 mg delamanid or 30 mg OPC-167832 and 400 mg BDQ, or 30 mg OPC-167832 and 300 mg delamanid and 400 mg BDQ will receive QD oral doses of IMP (OPC-167832 and/or delamanid and/or BDQ) from Day 1 through Day 14. Subjects receiving BDQ will take a loading dose of 700 mg BDQ on Day 1 and 500 mg on Day 2. The dose of BDQ will be 400 mg QD for days 3 to 14.

Delamanid (300 mg) should be administered orally once daily (QD), within 5 to 10 minutes after the completion of a meal.

OPC-167832 (30 mg QD) and BDQ should be administered orally, approximately 30 minutes after administration of delamanid.

The IMP will be administered with 240 mL of still (noncarbonated) water at room temperature.

Based on the Stage 1 PK/PD analysis of OPC-167832 plasma concentrations and reduction in log10CFU/mL, a dose lower than the current 30 mg specified in the protocol maybe considered, provided it can offer similar potential for efficacy as the 30 mg dose.

#### 3.2.2 Reference Product

# 3.2.2.1 Stage 1 and Stage 2

Subjects randomized to RHEZ will receive QD oral doses of RHEZ from Day 1 through Day 20.

Subjects will receive Rifafour® single-dose combination tablets. Each RHEZ tablet contains 150 mg rifampicin, 75 mg isoniazid, 400 mg pyrazinamide, and 275 mg ethambutol. Subjects will receive the following number of Rifafour tablets per day based on their pretreatment body weight:

- Subjects weighing 30 to 37 kg will receive 2 tablets per day.
- Subjects weighing 38 to 54 kg will receive 3 tablets per day.
- Subjects weighing 55 to 70 kg will receive 4 tablets per day.
- Subjects weighing > 70 kg will receive 5 tablets per day.

RHEZ will be administered with 240 mL of still (noncarbonated) water 1 hour prior to a meal or 2 hours after a meal.

### 3.3 Trial Population

Approximately 118 male or female subjects with newly diagnosed, uncomplicated, smear-positive, drug susceptible pulmonary TB who meet all the inclusion criteria and none of the exclusion criteria will be enrolled and randomized into this trial. In Stage 1, approximately 72 subjects will be enrolled and randomized to 1 of 4 cohorts (18 subjects per cohort). Approximately 46 subjects will be enrolled and randomized in Stage 2. Subjects who randomized to Stage 1 cannot enroll in Stage 2.

#### 3.4 Trial Visit Window

There is no visit window for trial visits on/before Day 20. The follow up visit can be target day plus or minus 3 days.

Statistical Analysis Plan

# 4 Sample Size

The trial is not powered for formal statistical hypothesis testing or comparisons. The sample size is based on sample sizes from several similar trials in the literature. It is planned to enroll 72 (18 in each cohort) subjects in stage 1 in 14:4 ratio. Stage 2 will enroll 46 patients in 14:14:14:4 ratio.

# 5 Statistical Analysis Sets

## 5.1 Efficacy Analysis Set

Efficacy analyses will be conducted based upon the Modified Intent-to-Treat (mITT) Analysis Set. The mITT Set will include randomized subjects who are agar media culture positive at baseline (either at day -2 or at day -1, or both), have taken any dose of IMP, and have available at least one post-baseline CFU count value.

Randomized Analysis Set includes subjects who are randomized into the study.

### 5.2 Safety Analysis Set

Safety Analysis Set includes subjects who are randomized and take any dose of IMP (OPC-167832 or Delamanid or Bedaquiline or RHEZ).

# 5.3 Pharmacokinetic Analysis Set

The PK Analysis Set will include all subjects who took at least one dose of IMP with adequate data for deriving the PK parameters accordingly to clinical pharmacology requirement.

# 5.4 Handling of Missing Data

Missing data in PK blood sample result and efficacy data will not be imputed for this study unless specified in individual sections. The imputation of missing colony forming units or LAM results will be discussed in corresponding sections.

# 6 Primary and Secondary Outcome Variables

# 6.1 Primary Outcome Variables

# 6.1.1 Efficacy - Stage 1

Efficacy will be assessed by the change in *Mycobacterium tuberculosis* bacterial (MTB) load in sputum as a measure of EBA. Bacterial load in sputum at each collection time point will be measured by colony-forming unit (CFU) counts on agar media culture. The

EBA will be measured as the slope of the change in log10CFU/mL on agar media from baseline (baseline is defined as the log10 of the mean of Day -2 and Day -1) to Day 14.

### 6.1.2 Pharmacokinetics - Stage 1

The following PK parameters will be determined for plasma OPC-167832:

- Day 1: Maximum (peak) plasma concentration (Cmax), time to Cmax (tmax), and area under the concentration-time curve (AUC) from time zero to time t (the last observable concentration) (AUCt).
- Day 14: Cmax during the dosing interval at steady-state (Cmax,ss), tmax, terminal-phase elimination half-life (t1/2,z), apparent clearance of drug from plasma at steady-state (CLss/F), AUCt, AUC calculated over the dosing interval at steady-state (AUCτ), accumulation ratio of Cmax (RCmax), and accumulation ratio of AUC (RAUC), Cmax normalized to dose (Cmax/Dose), and AUCτ normalized to dose (AUCτ/Dose).

### 6.1.3 Pharmacokinetics - Stage 2

The following PK parameters will be determined for plasma OPC-167832, delamanid and BDQ:

- Day 1: Cmax, tmax, and AUCt.
- Day 14:  $C_{max,ss}$ ,  $t_{max}$ ,  $t_{1/2,z}$ ,  $CL_{ss}/F$ ,  $AUC_{\tau}$ ,  $R_{Cmax}$ ,  $R_{AUC}$ , and  $C_{max}$  normalized to dose ( $C_{max}/Dose$ ), and  $AUC_{\tau}$  normalized to dose ( $AUC_{\tau}/Dose$ ).

# 6.1.4 Pharmacokinetics/Pharmacodynamics - Stage 1

The maximum effect ( $E_{max}$ ) and exposure producing 80% of  $E_{max}$  ( $EC_{80}$ ) for OPC-167832, regardless of dose level, will be determined from an exposure-response analysis of the decline of  $log_{10}CFU/mL$  counts on agar media. The results can be found in a separate population PK/PD analysis report.

#### 6.1.5 Pharmacokinetics/Pharmacodynamics - Stage 2

The  $E_{max}$  and  $EC_{80}$  for OPC-167832 in combination with delamanid and/or BDQ will be determined from an exposure-response analysis of the decline of  $log_{10}CFU/mL$  counts on agar media. The results can be found in a separate population PK/PD analysis report.

### 6.1.6 Safety and Tolerability - Stage 1 and Stage 2

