### 3.5 Endpoints

#### 3.5.1 Primary Endpoints

##### 3.5.1.1 Efficacy - Stage 1

Efficacy will be assessed by the change in TB bacterial load in sputum as a measure of EBA. Bacterial load in sputum at each collection time point will be measured by CFU counts on agar media culture. The EBA will be measured as the slope of the change in log-CFU from baseline (ie, the mean of the values from Day -2 and Day -1) to Day 14.

Protocol 323-201-00003

### 3.5.1.2 Pharmacokinetics - Stage 1

The following PK parameters will be determined for plasma OPC-167832:

- Day 1:  $C_{\max}$ , time to  $C_{\max}$  ( $t_{\max}$ ), and AUC from time zero to time t (the last observable concentration) ( $AUC_t$ ).
- Day 14:  $C_{\max}$  during the dosing interval at steady-state ( $C_{\max,ss}$ ),  $t_{\max}$ ,  $t_{1/2,z}$ , apparent clearance of drug from plasma at steady-state ( $CL_{ss}/F$ ),  $AUC_t$ , AUC calculated over the dosing interval at steady-state ( $AUC_{\tau}$ ), accumulation ratio of  $C_{\max}$  ( $R_{C_{\max}}$ ), and accumulation ratio of AUC ( $R_{AUC}$ ),  $C_{\max}$  normalized to dose ( $C_{\max}/Dose$ ), and  $AUC_{\tau}$  normalized to dose ( $AUC_{\tau}/Dose$ ).

### 3.5.1.3 Pharmacokinetics - Stage 2

The following PK parameters will be determined for plasma OPC-167832, delamanid, and BDQ:

- Day 1:  $C_{\max}$ ,  $t_{\max}$ , and  $AUC_t$ .
- Day 14:  $C_{\max,ss}$ ,  $t_{\max}$ ,  $t_{1/2,z}$ ,  $CL_{ss}/F$ ,  $AUC_{\tau}$ ,  $R_{C_{\max}}$ ,  $R_{AUC}$ , and  $C_{\max}$  normalized to dose ( $C_{\max}/Dose$ ), and  $AUC_{\tau}$  normalized to dose ( $AUC_{\tau}/Dose$ ).

### 3.5.1.4 Pharmacokinetics/Pharmacodynamics - Stage 1

The maximum effect ( $E_{\max}$ ) and exposure producing 80% of  $E_{\max}$  ( $EC_{80}$ ) for OPC-167832, regardless of dose level, will be determined from an exposure-response analysis of the decline of log-CFU count on agar media.

### 3.5.1.5 Pharmacokinetics/Pharmacodynamics - Stage 2

The  $E_{\max}$  and  $EC_{80}$  for OPC-167832 in combination with delamanid and/or BDQ will be determined from an exposure-response analysis of the decline of log-CFU counts on agar media.

### 3.5.1.6 Safety and Tolerability - Stage 1 and Stage 2

Safety and tolerability will be assessed based on the incidence of AEs and the incidence of abnormal findings in clinical laboratory tests (serum chemistry, hematology, urinalysis, and coagulation), physical examinations, vital signs, and electrocardiograms (ECGs).

Protocol 323-201-00003

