# 6.2 Secondary Outcome Variables

# 6.2.1 Efficacy

### Stage 1 and Stage 2

The slope of the change in log10LAM pg/mL values and the change in time to detection (TTD) in the Mycobacteria Growth Indicator Tube® (MGIT) system will be assessed from baseline to Day 14.

#### Stage 2

Efficacy will be assessed by the change in bacterial load in sputum as a measure of EBA. Bacterial load in sputum at each collection time point will be measured by CFU counts on agar media. The EBA will be measured as the slope of the change in log10CFU/mL from baseline (baseline is the log10 of the mean of the values from Day -2 and Day -1 with more details in Section 8.1) to Day 14 and compared with the administration of 30 mg OPC-167832 alone (data derived from Stage 1). Similar analyses are performed for log10LAM pg/mL and MGIT TTD endpoints.

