# 8 Efficacy Analyses

# 8.1 Primary Efficacy Endpoint Analyses

# 8.1.1 Stage 1

Overnight sputum will be collected starting from 3pm to 7am next day starting on Day -2, -1, 2, 4, 6, 8, 10, 12 and Day 14. *Mycobacterium tuberculosis* bacterial load in sputum at each collection time point will be measured by CFU counts on solid media culture. Two agar media bi-plates will be inoculated with 0.1 mL sputum sample per side (total of 0.2 ml per whole plate) at each visit. Each sample was diluted to  $1,10^{-1},10^{-2},10^{-3},10^{-4},10^{-5}$  times of the original concentration, represented by the values of dilution factor collected from CRF in 0, 1, 2, 3, 4, 5. The number of colonies from each plate collected in the CRF will be converted to CFU per mL using the formula: *Number of colonies collected from CRF*  $\times 10^{dilution factor collected in CRF+1$ . Because of the initial 10-fold dilution factor during sputum sample preparation, 1 is added to the power of 10. The CFU value reported from the laboratory is set to missing if the qualitative culture result is "Negative for MTB Complex" or "Contaminated". Because two results are collected per visit, the method to derive the analysis value for CFU for a visit day is described as follows:

If only one CFU result is available, then the available result is used as the CFU/mL value from that visit. If both CFU results are available, the average CFU/mL is taken as the value for that visit. If both sputum samples have missing CFU result, then the qualitative test result from SOLID MICROBIAL CULTURE will be taken into consideration. If both of the SOLID tests are "negative for MTB Complex", or if one of the SOLID results is "negative for MTB complex" and the other is "CONTAMINATED", the CFU for that visit is set to 5 CFU/mL, since the lower detection limit of the agar media is 5 CFU/mL. If both SOLID tests are "CONTAMINATED", then the CFU/mL for that visit is still treated as missing.

The baseline value derived for the analyses is as follows.						

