The study day of baseline is set to be 0 no matter whether the baseline comes from Day - 2 or Day -1 or the average. The derived analysis CFU is log10 transformed in the calculations of decline in bacteria load. The early bactericidal activity (*EBA*) is determined by the rate of decline in log10CFU/mL during the first 14 days of treatment. The rate of decline will be estimated using both a two-point calculation (day 14 and day 0 (baseline)) as well as a linear-regression based approach as discussed in Section 8.1.1.1.1 and Section 8.1.1.1.2.

and

Version Date: 16 May 2022

Protocol 323-201-00003

The effect size for EBA for IMP-1 group relative to that of IMP-2 group is expressed as the ratio of EBA as shown in formula (1). Either Fieller's method or Delta method as described in Sections 8.1.1.2  will be used in the estimation of the confidence interval of the ratio

$$\frac{EBA_{0-14,IMP1}}{EBA_{0-14,IMP2}}\tag{1}$$

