#### LAM:

More details of analysis data derivation for LAM is provided as follows.

Two LAM assessments are available at each visit, one on raw sputum (LAM(raw)), and one on processed decontaminated sputum (LAM(processed)). Baseline LAM is calculated as the average of Day -2 and Day -1 and the log10 of the average is used in EBA derivation. If one sample has a missing value then the nonmissing sample is used. The lower limit of quantification (LLoQ) of LAM test is 15 pg/mL. If a sample result has a reported value below the LLoQ (< 15 pg/mL) and does not indicate "NO RESULT", the value 15 pg/mL is used in the analyses for that visit.

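### Taking log10 of the two-day arithmetic mean at baseline, but log10 of a single day afterwards, biases the two-point CFU and LAM EBA upwards and pulls EBA ratios modestly toward 1

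*SAP*

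**What the plan says.** **CFU baseline.** SAP 6.1.1 (Stage 1, primary) takes log10 "of the mean of Day -2 and Day -1) to Day 14". SAP 6.2.1 repeats this order for Stage 2, again log10 "of the mean of the values from Day -2 and Day -1 with more details in Section 8.1". The detailed CFU derivation in SAP 8.1.1 is not legible in the public copy, but 6.1.1 and 6.2.1 both state the order.

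**LAM baseline.** SAP 8.2: "Baseline LAM is calculated as the average of Day -2 and Day -1", after which the log10 of that average enters the EBA.

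**Visit values.** Two plates are read from each overnight sputum, and SAP 8.1.1 says: "If both CFU results are available, the average CFU/mL is taken as the value for that visit". The derived CFU is then log10-transformed. This plate averaging is the same at Day -2, at Day -1 and at every later visit.

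**EBA and effect size.** SAP 8.1.1 places baseline at Day 0: "The study day of baseline is set to be 0 no matter whether the baseline comes from" Day -2, Day -1 or their average. The two-point EBA in SAP 8.1.1.1.1 is the fall in log10 from baseline to Day 14 per day. The effect size is a ratio of EBAs (Protocol 7.4.1.1.1; SAP 8.1.1).

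**Protocol baseline.** Protocol 3.5.1.1 describes "the slope of the change in log-CFU from baseline (ie, the mean of the values from Day -2 and Day -1" without saying whether the log comes before or after averaging. Protocol 7.4.1.1.1 calls baseline the average of the two days' measurements and applies log10 in equation (1).

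**The concern.** Baseline and follow-up are not on the same footing. The log of an arithmetic mean is never below the mean of the logs, and exceeds it whenever the two values differ. Baseline therefore sits systematically above the level that single-day log values estimate. The fall from baseline to Day 14 then includes an amount that has nothing to do with treatment.

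The plate averaging does not offset this, because it is identical at every visit; the extra averaging over two days happens only at baseline. Adding subjects does not remove the excess, and the Fieller and delta-method intervals do not allow for it.

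The ratio is what makes this matter. A constant added to both arms cancels from a difference but not from a quotient: weak doses look better relative to RHEZ than they are, and a regimen stronger than RHEZ looks less so. The trial rests on estimation and is not powered for testing, so these ratios are a main reported result.

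**Working it through.** **Inputs from the documents.** 14-day declines of 0.84 (delamanid 200 mg) and 1.44 (RHEZ) log10 CFU from Protocol 7.4.1.1.1; 14 subjects per OPC-167832 dose; RHEZ pooled over four Stage 1 cohorts, 4 × 4 = 16.

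**Assumed, because the documents do not give them.** The day-to-day SD *s* of a subject's single-day log10 value, 0.3 to 0.6; normality on the log scale; and the correlation ρ between the two baseline days, 0 or 0.5.

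**The plan's own figure.** 0.84/1.44 = 0.583, which reproduces the stated 58%.

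**Baseline excess.** With X₁ and X₂ the two days' log10 values around a common mean μ,

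b = E[log10((10^X₁ + 10^X₂)/2)] − μ = E[log10 cosh(ln 10 · (X₁ − X₂)/2)],

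where X₁ − X₂ has SD s√(2(1 − ρ)). This is positive for any s > 0 with ρ < 1. I evaluated it by Gauss-Hermite quadrature; a simulation of 400,000 subjects per SD agreed for ρ = 0.

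**Effect on EBA and ratio.** The two-point EBA gains b/14 per day. A ratio a/c of 14-day declines becomes (a + b)/(c + b).

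| ρ | s | b (log10) | b/14 per day | b/1.44 | 0.583 reads |
|---|---|---|---|---|---|
| 0 | 0.3 | 0.047 | 0.0034 | 3.3% | 0.596 |
| 0 | 0.4 | 0.079 | 0.0056 | 5.5% | 0.605 |
| 0 | 0.5 | 0.116 | 0.0083 | 8.0% | 0.614 |
| 0 | 0.6 | 0.157 | 0.0112 | 10.9% | 0.624 |
| 0.5 | 0.3 | 0.025 | 0.0018 | 1.7% | 0.590 |
| 0.5 | 0.6 | 0.087 | 0.0062 | 6.1% | 0.607 |

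With ρ = 0, an inert drug would show a ratio to RHEZ of b/(1.44 + b), that is 0.032 at s = 0.3 and 0.098 at s = 0.6, instead of 0. From the other side of 1, a true ratio of 1.5 reads 1.484 to 1.451. A hypothetical weak dose with a decline of 0.28 (true ratio 0.28/1.44 = 0.194) reads 0.327/1.487 = 0.220 to 0.437/1.597 = 0.274.

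**Against sampling error.** Counting within-subject error only, with ρ = 0, the variance of a subject's change is about 1.5s². The delta-method SE of the 0.583 ratio is 0.583 × √(1.5s²/(14 × 0.84²) + 1.5s²/(16 × 1.44²)), which gives 0.078 at s = 0.3 and 0.155 at s = 0.6. The shifts of 0.013 and 0.041 are 17% and 26% of one SE. For the 0.194 ratio they are 37% and 57% of one SE.

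**Regression slope.** In an ordinary least-squares slope over Days 0, 2, …, 14, the sum of squares about the mean day is 168 and the weight on Day 0 has size 7/168 = 0.0417. If baseline is a Day 0 response, the EBA gains 0.0417b per day, which is 14 × 7/168 = 58% of the two-point bias; 0.583 then reads 0.591 to 0.608 for s = 0.3 to 0.6 and ρ = 0.

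**After the change.** With the mean of the two log10 values as baseline, the expected excess is 0 for every s, and the worked ratio stays 0.583.

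**The case against.** Four points on the other side carry weight.

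*Dose-response.* A reader might infer that the bias flattens the Stage 1 dose-response and exposure-response. The documents do not support that. A common constant leaves every difference between doses unchanged in expectation; the absolute curve shifts, and only the ratio to RHEZ is compressed. Emax and EC80 come from a separate population PK/PD plan, whose baseline handling cannot be seen here.

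*Mixed model.* A reader might also take it as settled that the mixed-model EBA is biased. Protocol 7.4.1.1.2, which speaks of all time points from baseline, and the Day 0 rule in SAP 8.1.1 point to baseline being a response. The model specification in SAP 8.1.1.1.2 is incomplete in the public copy, however. If baseline is only a covariate, this bias does not enter the slope.

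*Departure from the protocol.* It is tempting to say that the SAP departs from the protocol. Protocol 3.5.1.1 leaves the order open, and equation (1) with its definition of baseline reads at least as naturally as the log of the average. The SAP may simply be carrying out the protocol, so both texts need the change.

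*Size.* The SD is assumed, and correlation between consecutive days reduces the excess. The shift is well below one standard error of the ratio, between-subject variation would widen that error further, and no success threshold is attached to the ratio. Redefining a primary baseline after Stage 1 has been analysed in an open-label trial has its own cost.

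These points limit the reach and urgency of the finding. They do not remove the systematic, avoidable excess in the two-point EBA.

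**Conclusion.** The concern holds for the two-point CFU and LAM EBA and for ratios built on it, in subjects with two usable baseline samples that differ. Subjects with one usable sample contribute no bias, and TTD, which is averaged and analysed on its own scale, is unaffected. The movement toward 1 assumes a positive comparator EBA and a similar excess in both arms; the latter is expected in randomised comparisons because the excess depends only on baseline variability.

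The direction is certain and the size is not. Under the assumed SDs and correlations, the protocol's example ratio moves by 0.01 to 0.04. The relative distortion is larger for weak doses. An effect on the mixed-model slope is conditional on baseline being a Day 0 response, and the 58% figure is a least-squares approximation. Nothing in the documents shows that a dose choice or a conclusion turns on a shift of this size. Severity is minor to moderate.

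**What to change.** Define the CFU and LAM baseline as the mean of log10(Day -2) and log10(Day -1), using the single available value when only one is usable. Make the change in SAP 6.1.1, 6.2.1, 8.1 and 8.2, and state the same order in Protocol 3.5.1.1 and with equation (1) in 7.4.1.1.1. If the mixed model takes baseline as a response, enter either the mean of the logs or the two log10 values as separate Day 0 records, and say which.

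If Stage 1 has already been analysed under the current definition, report both versions side by side rather than replacing one with the other.

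The cost is a wording change in two documents and a small programming change, with no new data. Reported EBAs become slightly smaller.
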